5.3. Safety evaluations

- Frequency of adverse events and serious adverse events by standardized DAIDS AE grading criteria (see appendix)

6. SELECTION AND ENROLLMENT OF SUBJECTS

6.1 Study Population

Healthy adults ages 18-64 with molecularly confirmed SARS-CoV-2 infection (COVID-19 disease) who are not currently admitted to a hospital will be eligible for participation in this study.

6.2 Inclusion Criteria

Patients must fulfill all of the following inclusion criteria to be eligible for the study:

1. Age \geq 18 years and \leq 75 years at the time of the assessment
2. Able and willing to understand the study, adhere to all study procedures, and provide written informed consent
3. Diagnosis of COVID-19 disease:
 - a. If symptomatic, presence of mild to moderate symptoms without signs of respiratory distress, with FDA-cleared molecular diagnostic assay positive for SARS-CoV-2 within 72 hours from swab to the time of commencing informed consent:
 - b. If asymptomatic, initial diagnosis of SARS-CoV-2 infection with positive FDA-cleared molecular diagnostic assay obtained no more than 72 hours from initial swab to the time of commencing informed consent

6.3 Exclusion Criteria

1. Patients who are hospitalized for inpatient treatment or currently being evaluated for potential hospitalization at the time of initiation of informed consent
2. Patients with a known allergy to Peginterferon Lambda-1a or any component thereof

3. Display symptoms of respiratory distress (Respiratory rate >20, room air oxygen saturation of <94%).
4. Participation in a clinical trial with or use of any investigational agent within 30 days before screening
5. Treatment with interferons (IFN) within 12 months before screening
6. Previous use of Peginterferon Lambda-1a
7. History or evidence of any intolerance or hypersensitivity to IFNs or other substances contained in the study medication.
8. Female patients who are pregnant or breastfeeding. Male patients must confirm that their female sexual partners are not pregnant.
9. Current or previous history of decompensated liver disease (Child-Pugh Class B or C) or hepatocellular carcinoma
10. Co-infected with human immunodeficiency virus (HIV)
11. Any of the following abnormal laboratory test results at screening:
 - a. Platelet count <75,000 cells/mm³
 - b. Absolute neutrophil count <800 cells/mm³
 - c. Hemoglobin <11 g/dL for women and <12 g/dL for men
 - d. Serum creatinine concentration $\geq 1.5 \times$ ULN and creatinine clearance (CrCl) < 50 mL/min by Cockcroft-Gault
12. History of liver disease other than viral hepatitis
13. Prior history or current evidence of any of the following:
 - a. Immunologically mediated disease that is uncontrolled
 - b. Retinal disorder or clinically relevant ophthalmic disorder
 - c. Any malignancy (excluding non-melanoma skin cancer) within 5 years before screening
 - d. Cardiomyopathy or significant ischemic cardiac or cerebrovascular disease.
 - e. Chronic uncontrolled pulmonary disease
 - f. Pancreatitis
 - g. Severe or uncontrolled psychiatric disorder
 - h. Active seizure disorder
 - i. Bone marrow or solid organ transplantation
14. Other significant medical condition that may require intervention during the study
15. Concurrent use of any of the following medications:
 - a. Therapy with an immunomodulatory agent
 - b. Current use of heparin or Coumadin
 - c. Received blood products within 30 days before study randomization
 - d. Use of hematologic growth factors within 30 days before study randomization
 - e. Systemic antibiotics, antifungals, or antivirals for treatment of active infection within 24 hours before study randomization
 - f. Any prescription or herbal product that is not approved by the investigator
 - g. Long-term treatment (> 2 weeks) with agents that have a high risk for nephrotoxicity or hepatotoxicity unless it is approved by the medical monitor
 - h. Receipt of systemic immunosuppressive therapy within 3 months before screening

6.4. Identification and Recruitment of Participants

Flyers will be handed out to anyone being tested at Stanford testing sites (ER, drive-through tent, and occupational health), inviting them to call us should their test turn positive. We plan to have personnel at the testing site handing out the flyers. Currently, Stanford's blood testing sites are identifying 30-50 newly diagnosed patients per day, the great majority of whom are not admitted. We are hoping to identify two COVID patients per day. If recruitment is slow in the first week, we will also advertise for newly diagnosed COVID cases on social media and hand out flyers at other screening sites as possible. We are also exploring the possibility of calling all COVID positive patients directly; this recruitment approach will be added to an amended protocol if we find it is possible.

6.5. Phone Screening Interview

Individuals who provide informed consent to be contacted after testing COVID-19 positive via the emergency department or occupational health will be contacted by phone. At the initial phone call, we will screen for inclusion and exclusion criteria; the clinical research coordinator (CRC) will fill out the RedCap screening form and determine if the subject is eligible and interested in participating. If the patient meets the criteria in the phone interview, we will invite them to the clinical research site (Stanford University) where we will review inclusion criteria again at the first patient visit. The subject will also be asked to bring in their proof of infection with them or to have it accessible in on-line form.

6.6. Study Enrollment Procedures and Baseline Evaluation

At the initial intake visit, screening eligibility criteria will be reviewed and confirmed. Subjects will undergo a standardized history, including time since symptom onset, and physical examination and have blood collected by phlebotomy. We will conduct the laboratory screening with complete blood count (CBC), comprehensive metabolic panel (CMP) and, in premenopausal women, beta HCG. Additional blood will be collected for biobanking. Inclusion/exclusion labs will be performed stat in the clinical lab. Participants will be asked whether they are enrolled in another study; they cannot be enrolled in other studies of investigational agents. After initial screening, the participant will then provide written informed consent to participate in the study and for the future use of biological specimens.

6.6. Potential Limitations on Recruitment and Mitigation Strategies

Given the fast-changing landscape during the COVID-19 pandemic, potential alterations are considered to mitigate the impact of newly identified therapies that change the standard of care and/or slower than planned enrollment. The study team plans to evaluate the rate of enrollment two weeks after enrollment opens. If fewer than 10 patients have been enrolled within the first two weeks, a potential solution to increase enrollment is to change the randomization ratio to be 2:1 on treatment:control. We have selected a 1:1 ratio under the assumption of equipoise; however, we anticipate that participants may not want to have a 50% chance of being randomized to placebo. To address this concern, we could increase the ratio in order to reduce the chance of being randomized to placebo to 33%. Under the assumptions described in our sample size estimates (Section 12.6 below), the change in the randomization ratio will not require a larger sample size.

7. CONCURRENT MEDICATIONS

7.1 Allowed medications and treatments

- a. Acetaminophen
- b. Ibuprofen or other non-steroidal anti-inflammatory medications
- c. Symptomatic care for cough/URI (e.g., decongestants/cough syrups)

7.2 Prohibited medications and treatments

- a. Other investigational and/or immunomodulatory agents for treatment of COVID-19, including but not limited to chloroquine or hydroxychloroquine.
- b. Heparin or coumadin

8. STUDY TREATMENTS

8.1 Method of assigning subjects to treatment groups

Up to 120 eligible patients will be randomly assigned to Lambda or placebo in a 1:1 ratio to the treatment and control arms using a REDCAP-based computer-generated randomization scheme developed by the study data management provider. Randomization will be stratified by age ($>=50$ and <50 years old) and sex. The investigator or designee will complete a password-protected electronic spreadsheet containing the randomization allocation, along with the code used to generate the allocation along with the seed used in the random number generation, will be stored on secure servers at Stanford.

8.2 Blinding

Administration of all study drugs will be single-blind (blinded to the study participant). All doses of study drugs will be prepackaged by the investigational pharmacist and administered by a study nurse not involved in data analysis. The study biostatisticians will be blinded to subject randomization, with the exception of an unblinded subgroup who will generate the randomization scheme and perform unblinded interim analyses. The subgroup will not discuss the unblinded data or interim results with the blinded biostatisticians and will save their materials on a server that is inaccessible to the blinded members. This study blind will be broken on completion of the clinical study and after the study database has been locked. During the study, the blind may be broken **only** in emergencies when knowledge of the patient's treatment group is necessary for further patient management. When possible, the Investigator should discuss the emergency with the data safety and monitoring board prior to unblinding.

8.3 Formulation of test and control products

8.3.1 Formulation of test product

Peginterferon Lambda-1a (Lambda), 180 mcg, administered as a single subcutaneous injection

8.3.2 Formulation of control

A 0.45mL normal saline in 1 mL syringe sealed with red cap (prevent leaking during transport)
The placebo syringe product will not match the test product.

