1. PROTOCOL SYNOPSIS

Study Title	A Phase 2 Randomized, Single-Blind Study of a Single Dose of Peginterferon Lambda-1a (Lambda) Compared with Placebo in Outpatients with Mild COVID-19
Sponsor	Stanford University
Description	Single-blind randomized controlled trial
Study Objectives	
 1. To evaluate the efficacy of subcutaneous (SC) injections of a single dose of 180 mcg of Peginterferon Lambda-1a compared with placebo in reducing the duration of viral shedding of SARS-CoV-2 virus in patients with uncomplicated COVID-19 disease. 2. To evaluate the efficacy of subcutaneous injections of a single dose of 180 mcg of Peginterferon Lambda-1a compared with placebo, in reducing SARS-CoV-2 viral loads and the duration of symptoms, hospitalizations, or ED visits in patients with uncomplicated COVID-19 disease. 3. To evaluate the safety and tolerability of subcutaneous injections of a single dose of 180 mcg of Peginterferon Lambda-1a compared with placebo.

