4. STUDY DESIGN

4.1 Study overview

This is a single center, open-label randomized controlled trial. Each subject will be administered either a single subcutaneous dose of study drug or placebo.

Screening data will be reviewed to determine subject eligibility. Subjects who meet all inclusion criteria and none of the exclusion criteria will be entered into the study

The following treatment regimens will be used:

- Experimental treatment: Peginterferon Lambda-1a, 180 mcg subcutaneous
- Control treatment: Normal saline, 0.45 mL subcutaneous

The duration of participation for each individual will be up to 28 days, with optional follow-up to 10 months following randomization. The planned duration for the entire study is 12 months.

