8.3.3 Packaging and labeling

Lambda Injection is a sterile, nonpyrogenic, ready-to-use (RTU) solution (0.4 mg/mL) that is clear to opalescent, colorless to pale yellow, and essentially free of particles. Lambda Injection is provided in a 1-mL long Type I glass syringe (0.18 mg/syringe) with a staked 29-gauge, 1/2-

inch, thin-walled needle. The syringe has a rigid needle shield and is stoppered with a plunger stopper. Syringes are prefilled with a solution of Peginterferon Lambda-1a drug substance, L-histidine, mannitol, polysorbate 80, hydrochloric acid, and water for injection and for a single use only.

Normal saline injection is a sterile, nonpyrogenic solution that is clear and will be provided in a 1 ml BD plastic syringe with a ½ inch, thin-walled needle with safety shield. Syringes are prefilled with a 0.9% sodium chloride solution and for a single use only. The injection will be prepared by the Stanford Investigational Pharmacy.

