8.4.4 Administration instructions

Lambda syringes are marked with dose indicator lines, which are used as a reference point for administering the correct dose. The clinician will expel the air bubble from the syringe and set the dose by aligning the front edge of the stopper with the correct dose indicator line. A sufficient overfill is included in each syringe for needle/syringe, dose adjustment, and bubble expulsion losses, leaving a sufficient amount of Lambda Injection for delivery of up to 180 mcg.

Both lambda and normal saline will be administered subcutaneously in either the lateral or posterior aspect of the upper arm or thigh. Injection sites should be clean and free of infection, skin lesions, scars, birthmarks, bony prominences, and large underlying muscles, blood vessels, and nerves. A lifted skinfold technique (pinching or bunching the skin) will be used to lift the subcutaneous layer away from underlying muscle, and the skin will be cleaned with an alcohol-impregnated swab before injection at a 90° angle.

Following study drug administration, participants will be observed in the study clinic for thirty minutes to assess for any adverse events.

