## 1 STUDY DETAILS

### 1.1 Study design

This phase 2 randomized, single-blind study intends to evaluate the efficacy of a single dose of peginterferon lambda-1a in outpatients with mild COVID-19 compared with placebo in reducing the duration of shedding of SARS-CoV-2 virus.

One hundred and twenty (60 per arm) enrolled patients will be randomized in a 1:1 fashion. Thus, there will be two arms: (1) the control arm, comprised of placebo in addition to standard supportive care and (2) the treatment arm, comprised of a single dose of peginterferon lambda-1a in addition to standard supportive care. An interim analysis for safety and overwhelming efficacy will be performed once 50% of patients have 24 hours of follow-up complete.

The primary analysis is based on intent-to-treat principles in that all patients who are randomized to study arm are included in the analysis, where cessation of shedding is assessed according to randomized study arm. The secondary analysis of adverse events (AE) are assessed according to dose received.

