### **2.4 Secondary efficacy analyses**

Time to resolution of all symptoms will be defined as the time from randomization until the first study day in which no symptoms are reported. The distribution of time to resolution of symptoms will be estimated using the Kaplan-Meier method, and Kaplan-Meier curves will be presented for each treatment arm. Time to symptom resolution at the end of the study period along with 95% confidence intervals will be presented for each treatment arm. The hazard ratio for resolution of symptoms will be estimated, along with its 95% confidence intervals, from a Cox proportional hazards model adjusted for age and sex.

We will model SARS-CoV-2 viral load in oropharyngeal tests over time using a generalized mixed effects linear regression model with a random effect for study participant to account for correlation within a participant. Viral load with cycle threshold (Ct) values above the limit of detection will be calculated by substituting a Ct value of 42 into the equation  $10^{(Ct - 42) * 0.23}$  to derive viral load from Ct. A logarithmic transformation on viral load will be fit to treatment arm, time, armXtime, and adjusted for age and sex to account for therandomization stratification variables. The armXtime interaction term will allow us to assess whether the trajectory of viral load differs by treatment arm. Time will be defined as days from randomization and, depending on model fit, will either be modeled continuously or with a flexible approach allowing a non-linear trajectory for the change in viral load over time. Model fit will be assessed based on visual inspection of the residuals. Alternative transformations or generalized linear models with a link function besides the identity link will be considered if the model does not fit the data well.

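### The participant blind is not secured as written: the syringes are visibly unmatched, no step conceals them, and Protocol section 4.1 calls the trial open-label

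*Protocol*

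**What the plan says.** On the design label, the Protocol synopsis has "Single-blind randomized controlled trial" and SAP section 1.1 begins "This phase 2 randomized, single-blind study". Protocol section 8.2 says that the person blinded at administration is the participant. Protocol section 4.1 says "This is a single center, open-label randomized controlled trial".

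On the products, Protocol section 8.3.2 says "The placebo syringe product will not match the test product". Section 8.3.3 puts Lambda in a long glass syringe with a fixed needle and a rigid shield, and allows the liquid to be opalescent or pale yellow. For the control it says "Normal saline injection is a sterile, nonpyrogenic solution that is clear and will be provided in a 1 ml BD plastic syringe". Section 8.3.2 adds a red cap for transport.

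On handling, section 8.4.4 says "Lambda syringes are marked with dose indicator lines, which are used as a reference point for administering the correct dose" and has the clinician expel air and set the dose. It gives no equivalent step for saline. The text common to both arms covers injection site and technique. The safeguards in section 8.2 are prepackaging by the pharmacist, a nurse who takes no part in data analysis, and blinded statisticians.

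On the outcomes, Protocol section 9.1.1 has participants complete a symptom questionnaire at home each day through Day 28. SAP section 2.4 builds a secondary endpoint on it: "Time to resolution of all symptoms will be defined as the time from randomization until the first study day in which no symptoms are reported".

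**The concern.** A saline placebo earns its place in this trial only if participants do not know what they received. The protocol concedes that the products look different, yet none of its stated safeguards acts on what the participant sees, and the participant is the one person section 8.2 says is blinded at administration. Section 4.1 then contradicts the claim of blinding altogether.

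A participant who works out the arm may score symptoms differently, decide differently about going to an emergency department, or report adverse events differently. The arm contrast on those outcomes would then mix expectation with drug effect. Neither document asks participants what they believe they received, so if the question were raised later there would be no data to answer it.

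**Working it through.** The plan states no figure on this point, so the check is mainly of text against text.

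**Step 1. What differs between the products (Protocol sections 8.3.2, 8.3.3, 8.4.2 and 8.4.4).**

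| Feature | Lambda | Saline |
|---|---|---|
| Barrel | Long 1 mL glass, with dose lines | 1 mL plastic |
| Needle | Staked, rigid shield | Safety shield |
| Closure in transport | Rigid shield | Red cap |
| Liquid | May be opalescent or pale yellow | Clear |
| Dose-setting step | Described | Not described |
| Volume | 0.18 mg ÷ 0.4 mg/mL = 0.45 mL | 0.45 mL |

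The nominal volume is matched. The mismatch lies in container, needle, closure and possibly liquid colour. On handling, the documents show only that a step is written for one arm and not for the other.

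**Step 2. What stands between the syringe and the participant.** Of the safeguards in section 8.2, prepackaging is done at the pharmacy, and the rules on the nurse and the statisticians protect the analysis. Neither document mentions an opaque sleeve, a drape, preparation out of sight, or an instruction to look away. The permitted sites are the lateral or posterior upper arm or thigh. Some of these are outside the participant's normal view and some are not.

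**Step 3. Which endpoints depend on the participant's knowledge.**

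- Largely protected: the primary endpoint (qRT-PCR on oropharyngeal swabs taken at visits, Protocol sections 5.1 and 9.1.2) and the oropharyngeal viral-load and AUC endpoints (SAP section 1.3). Knowledge of the arm could reach these only indirectly, through attendance or dropout.
- Exposed: time to symptom resolution (secondary); sustained, respiratory and systemic resolution and the cough and breathlessness component of progression (SAP sections 1.4 and 2.5, exploratory); emergency visits, which are partly the participant's decision; and adverse events that rely on the participant's report.

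**Step 4. A hypothetical scale.** Suppose there is no true effect on symptoms, but knowledge of the arm multiplies the daily rate of reporting no symptoms by a ratio r in one arm. With 1:1 allocation and d events, the log-rank or Cox statistic is approximately normal with mean ln(r) × √(d/4) and variance 1. A two-sided 5% test then rejects with probability P(|N(ln(r)√(d/4), 1)| > 1.96). For r = 1.2 and d = 80, the mean is 0.182 × 4.472 = 0.815, and the rejection probability is 0.126 + 0.003 = 0.129.

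| r (assumed) | d = 80 (assumed) | d = 100 (assumed) |
|---|---|---|
| 1.1 | 7.1% | 7.6% |
| 1.2 | 12.9% | 14.9% |
| 1.3 | 21.7% | 25.9% |

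Neither r nor d comes from the documents. The table shows how sensitive such a test would be. It does not estimate the bias in this trial.

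**The case against.** The strongest reply is that unmatched syringes do not unblind anyone by themselves. Each participant has one injection, never sees the other product, and would have to both see the syringe and know what each looks like. Single-blind also allows the nurse to know the arm. The consent text was not among the documents reviewed, so what participants are told about appearance is unknown. All of this stands, and it limits the point to a blind that is unprotected.

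Several stronger readings are tempting, and the documents do not support them:

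- *The blind must fail.* No passage says that the barrel, label or shield is in view during the injection. That would be an inference from silence.
- *The dose is set differently in the two arms.* Section 8.4.4 describes the step for Lambda and is silent on saline. Silence does not establish a difference.
- *The trial is really open-label.* Section 4.1 conflicts with three other places. That is a contradiction to resolve and does not show that participants will be told their arm.
- *Side effects will reveal the arm.* Protocol section 2.2 reports flu-like symptoms in 64.3% and arthralgia or myalgia in 50.0%, but in 14 hepatitis delta patients in a 48-week study. This trial gives one dose. The same section reports only mild events in one healthy-volunteer study and 9.9% pyrexia with 180 µg Lambda plus ribavirin, and section 10.1.2 notes that mild and moderate symptoms are hard to tell from COVID. This route is possible but weakly evidenced, and concealing the syringe would not close it.

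The direction of any bias is also unknown. Expectation could shorten reported symptoms on Lambda while flu-like reactions lengthen them. For emergency visits and hospitalizations, SAP section 2.4 plans only incidence by arm with confidence intervals, although Protocol section 12.4 plans a regression comparison, so how much a biased contrast would matter there depends on which is followed.

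**Conclusion.** The point holds in a limited form. Three facts rest on plain text: the design label is contradictory, the syringes are unmatched by the protocol's own statement, and neither document describes a step that hides the syringe from the participant or a check on the blind. It follows that participant blinding is asserted but not secured, and that the self-reported outcomes are open to bias.

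It does not follow that the blind will fail or that the primary result is compromised. The size of any bias cannot be derived from the documents. The range of about 7% to 26% is hypothetical on both inputs and also assumes a constant shift in one direction. The conclusion does not depend on it. This is an inexpensive improvement to the secondary, exploratory and safety evidence.

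**What to change.** 1. Reconcile Protocol section 4.1 with section 8.2, the synopsis and SAP section 1.1, so that all four give the same blinding status. Items 2 and 3 apply if that status is single-blind.
2. In section 8.4.4, require the following in both arms: the syringe is uncapped and prepared out of the participant's sight; the barrel is covered by an opaque sleeve or label; and the injection is given behind a drape or with the participant looking away.
3. During the 30-minute observation already required by section 8.4.4, ask each participant once which treatment they think they received, with an optional repeat at Day 28. Tabulate the answers by arm. The early answer mainly reflects what was seen at the injection, on the assumption that few reactions start so soon, since the documents give no onset times. A Day 28 answer would also reflect reactions and recovery.

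Use the guess for description only. It is measured after randomization, so adjusting for it or stratifying by it would undermine the randomized comparison. If the blind had failed, guess and arm would nearly coincide and the adjusted analysis would say little.

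The cost is some extra handling at one injection, one or two questionnaire items, one table and the protocol wording. No new product, visit or staff is needed. The downside is that the table may show the blind to have been imperfect.
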